4.2 SUBSTUDIES (IF APPLICABLE)

N/A

5 STUDY ENROLLMENT AND WITHDRAWAL

The sample size for the overall study will be 20 outpatient hemodialysis clinics with approximately 1,200-1,440 patients in total. For the peer mentoring intervention, sample size will be 30 patients at each of 10 clinics randomized to receive the peer mentoring (n=300).

5.1 SUBJECT INCLUSION CRITERIA

We aim to include all non-vulnerable in-center patients at the 20 participating hemodialysis facilities. The trial is designed so as not to exclude anyone, including women and minorities to the extent they are represented at the dialysis facilities from the ages of 21 and older.

5.2 SUBJECT EXCLUSION CRITERIA

We will only exclude those who have opted out of the study and vulnerable patients: those under 21 years of age, prisoners, those with poor cognition or cognitive impairment, and those deemed vulnerable based on cognitive impairment by the Clinical Manager, Medical Director, and/or Social Worker (see Table 3: Screening for Patient Vulnerable Status), and those who are unable to comprehend the patient information sheet due to lack of facility in English or Spanish (patients whose primary spoken language is not English or Spanish). Due to limited availability of peer mentors fluent in languages other than English, only English-speaking patients will be offered peer mentoring.

5.3 STRATEGIES FOR RECRUITMENT AND RETENTION

In order to recruit facilities, the FMCNA Project Manager has approached/will approach regional management (regional vice presidents, RVPs) at FMCNA to educate them regarding the study process. After screening of facilities by FMCNA based on inclusion criteria and random selection by UM from the pool of eligible facilities, these RVPs were/will be approached and their approval sought, on a voluntary basis. At that time, RVPs have assessed/will assess whether facilities were/are adequately staffed to participate in the study and have considered/will consider the level of staff effort required in the context of other ongoing FMCNA and CMS initiatives. RVPs have management authority over their regional clinics and were/will be able to facilitate clinic recruitment. The RVP or the FMCNA Project Manager has approached/will approach the medical director of the randomly-selected facilities, and each facility's management body (called Governing Body) will approve study participation.

If a facility declines to participate, we will approach the next randomly-selected facility until the recruitment goal for the region is reached. Once recruited, facilities will also be randomized into study arms. If a facility drops out of the trial, the UM team will select another eligible facility to participate in the trial according to the clinic inclusion criteria and recruitment process used for the initial clinics.

We plan to include all non-vulnerable patients at participating dialysis facilities who do not opt out of the study. The study population of patients enrolled in this trial will be representative of the general adult hemodialysis population in the United States with respect to age and health status (e.g., typically with multiple comorbid conditions, including diabetes, hypertension, and cardiovascular disease). Our target subject sample is approximately 1,200-1,440 patients across the 20 facilities will be enrolled in the study (see attached Performance Site Listing). It is anticipated that there will be more than adequate representation by minorities as these are typically over represented in the dialysis population and also because of the geographic diversity of participating sites (e.g., Michigan, Ohio, California, Alabama, Massachusetts and Connecticut). Health care providers will not be study subjects.

As is described in this IRB application, we are seeking Institutional Review Board approval for a waiver of consent and waiver of HIPAA authorization based on the study's minimal risk to patients. There will be an opt out process for the Dialysafe Study to meet ethical obligations to patients, including respect for patient decision-making and a patient-centered approach to research. Thus, each patient will have the opportunity to **opt out of having their data used in the study, and from being offered peer mentoring if their facility is randomized to the intervention and if they are randomly selected to be offered an opportunity to participate in the patient activation intervention**. The University of Michigan is responsible for the opt out process for patients, although it will be implemented by FMCNA staff. Under the direction of, and with remote support from, a UM study coordinator, each patient will be given an information sheet by FMCNA staff, using a script to be approved by the IRB. The UM study coordinator will be available for further explanation of the study and to answer questions, and will monitor and check messages at, the toll-free number included in the patient information sheet. Facility staff will record that each patient has received the information sheet, and if they have verbalized a decision to opt out of the study. The information sheet will also provide a 1-800 telephone number to call in order to learn more about the study and opt out of the study if desired (see attached Help Line scripts). Any patient opt outs received through the toll-free number while the UM coordinator is off-site will be securely transferred to FMCNA. A master list will be maintained of all patients informed about the study, and those who have opted out. One week will pass to allow patients an opportunity to opt out before starting the study. Thereafter, patients may opt out at any time. Enrolled (patients who do not opt out) will have study data shared with UM-KECC along with the FKC ID1 unique identifier. If patients do not opt out, no further action is required from patients to have their data used in the study.

A randomly-selected subset of patients in facilities randomized to the patient activation intervention arm will be offered the opportunity to participate in the intervention. A list of patients who have not opted out of the study will be provided by FMCNA to UM School of Information staff in a secure computing environment, SharePoint. This list will include only the information needed to contact patients (first/last name, sex, clinic name/clinic ID, treatment day/shift, primary/alternate phone). Patients who are randomly selected will be contacted by a UM Study Coordinator on a non-dialysis day by phone to offer them the opportunity to participate using a designated script. If the UM Study Coordinator cannot reach the patient after 5 calls, they will ask the Study Champion to follow up with the patient to gauge interest. In the event that a

patient is interested in joining the peer mentoring program but does not have regular access to a phone to contact UMSI study staff and/or NKF, a pre-paid cell phone will be provided for the patient to use. The phone will be shipped to the patient's home address with a limited number of minutes pre-loaded for their use. At the end of the study, the phone may be discarded, or the patient may choose to purchase more minutes and retain the phone as a personal device. The pre-paid phone is not considered an incentive because it will not be preloaded with enough minutes to be used for personal use. The estimated value of the phone without minutes is \$25. Neither study nor clinic staff will have the ability to track the phone's use after it has been activated by the patient.

Patients may also be contacted by a "patient advocate," a current in-center dialysis patient who will be identified by their clinic staff as a potential advocate for the peer mentoring program who is already enrolled in the peer mentoring program. As in the Operations Committees, clinic staff will identify potential advocates. UMSI staff will contact potential patient advocates using the contact information they have for the peer mentoring program, and invite them to be a patient advocate, emphasizing that the role is voluntary. If an individual agrees to be a patient advocate, UMSI study staff will ask clinic staff to provide the patient with the Patient Advocate Agreement (See "Patient Advocate Agreement" document) for signature, provide a copy of the signed agreement to the patient advocate, and upload the signed document to a secure Sharepoint. UMSI study staff will conduct a 15 minute phone call with advocates to describe their role and answer any questions or concerns. (See "Patient Advocate Discussions" document for advocate training plan.) Patient advocates may discuss their experience in the peer mentoring program with other patients in their clinic, participate in "lobby days" as approved and facilitated by their local clinic staff, and direct any interested patients to contact the UMSI study staff to learn more about joining the peer mentoring program. Patient advocates will not consent any patients for the peer mentoring program (see "Patient Advocate Discussions" document for the scope of the patient advocate role; see "Peer Mentor Program Flyer" for handout in clinic). Up to three Patient Advocates may be recruited for each shift in the clinic. Data for patients who agree to participate in the patient activation intervention will be entered into the HIPAA-compliant, web-based peer mentoring management system for intake by the National Kidney Foundation. Those who refuse will be recorded on the patient list located in the FMCNA SharePoint environment (see attached document, *HIPAA Compliance of Dialysafe Tools*).

Retention of participants in patient activation intervention. While participant retention is an issue in virtually any trial, dialysis patients are likely to experience fatigue, pain and other symptoms; thus there is a greater than average risk of patients not completing the intervention. In the two aforementioned published studies regarding peer mentoring and coaching for hemodialysis patients, participant retention rates were 85.7% for the 2-4 month study and 100% for the 10-week study, respectively.^{18, 153} Another study involving one-to-one peer support to people with diabetes had a 75.7% retention rate for a study that was 8-12 months long.¹⁵⁴ Notably, all of the aforementioned studies were more demanding than ours in terms of numbers of sessions with patients (8-30 sessions). Therefore, based on these prior studies, but recognizing the uncertainties of the COVID-19 pandemic, we estimate a retention rate of at least 73% for the peer mentoring intervention. In summary: if 60 patients in a facility are offered peer mentoring, we predict that approximately 30 of them will agree to receive peer mentoring; of these patients, at least 22 will complete the entire intervention. Under this circumstance, an additional 8 will thus complete part of the intervention.

In order to achieve our estimated retention rate of 65-75% for the complete intervention, and in keeping with published research,¹⁵⁵ our study team will use a combination of retention strategies. The following general evidence-based retention strategies will be used in

combination: patient/community involvement;¹⁵⁶ offering participant incentives;¹⁵⁶ using a participant-tracking database¹⁵⁷; using systematic methods for participant contact and scheduling of peer mentoring appointments;¹⁵⁶ issuing reminders prior to appointments;¹⁵⁶ interpersonal skill training for project staff;¹⁵⁷ monitoring retention;¹⁵⁶ and monitoring satisfaction with the study¹⁵⁸ via the planned peer mentoring survey.

Furthermore, we will follow best practices for retaining older and seriously ill study participants including: demonstrating care for participants by sending birthday or holiday cards;¹⁵⁸ flexibility in scheduling and dividing up peer mentoring sessions over time¹⁵⁸; facilitating home-based participation in the study;¹⁵⁸ developing a protocol for managing missed follow-ups;¹⁵⁸ and keeping response burden for patient data collection very low.¹⁵⁹

5.4 TREATMENT ASSIGNMENT PROCEDURES

5.4.1 Randomization Procedures

The 20 hemodialysis facilities will be randomized to the four intervention combinations of the 2x2 factorial design, assigning 5 facilities to each of the 4 combinations (both provider education and patient activation using peer mentoring; provider education alone; patient activation alone; and neither intervention). Facilities will be stratified by geographic region and socio-economic status to ensure treatment balance on those factors.

With regard to peer mentoring only, we will randomly select patients who are not vulnerable and have not opted out of the study in succession, until approximately 30 English-speaking patients in a facility accept peer mentoring. Patient randomization will be stratified by treatment shift. Every time a patient declines to participate, we will choose another patient randomly until the enrollment target is reached. Patients entering a facility randomized to the patient activation intervention during weeks 1-18 of the 24-week intervention period will be added to the list of patients eligible for peer mentoring from which patients are randomly selected for peer mentoring. We anticipate that 15-20% of patients in the study facilities will be replaced by new patients during the 11-month study period due to mortality, change in ESRD treatment modality (e.g., a kidney transplant), or changing facilities.

5.4.2 Blinding Procedures

Study participants and facilities will not be blinded to treatment status. However, during the initial analyses, study analysts will be blinded to treatment status in that they will not know which facilities are in which intervention group. Each intervention group will be given a non-identifying code, and each facility assigned to one of those codes (e.g., group A, group B, group C) while a list of facilities by treatment status is kept separate during the analyses. Analyses will then be conducted using intervention group codes that do not reveal which intervention in which a facility is participating. Supplementary as-treated analyses cannot practically be completed in a blinded fashion due to heterogeneity of measures (e.g., number of peer mentoring sessions completed by a patient).

5.4.3 Reasons for Withdrawal

Because ours is an educational intervention with support from the dialysis facility's parent organization, we expect facility attrition to be very low. Nevertheless, if facilities do drop out

during the intervention phase, they will be replaced and the intervention will take place at a new facility. A facility would need to be replaced if: 1) they request to leave the study; or 2) 75% of the staff do not complete at least 90 minutes of the training within the first 14-16 weeks of the intervention period.

As for missing outcome data for facilities in the study, data for our primary outcome as well as two secondary outcomes (fluid adherence/Interdialytic weight gain and dialysis session adherence) are gathered at the dialysis session level, using data that are automatically gathered when treatment is delivered.

With IRB waiver of consent and waiver of HIPAA authorization with an opt out process, we expect that we will not have significant attrition due to patient withdrawal since interventions will be provided at the facility-wide level. Attrition may be seen in the patient activation (peer mentoring) intervention if patients choose not to participate in the peer mentoring program or if patients drop-out after starting the program.

A final type of attrition may be the possibility of missing data due to patients not completing the self-reported quality of life (KDQOL) survey or the patient symptom question regarding recovery time. For example, some participants may refuse to answer certain questions or may miss follow-up surveys. Where possible, we will note reasons for missing data by triangulating data sources to determine whether a patient has moved to another facility, or in accordance with two of our outcomes, been hospitalized or die. Although every effort will be made to collect these data, some missing surveys are still likely, particularly among those in ill health. We do not expect missing surveys to be associated with study arm, but missingness itself can be analyzed for treatment differences as a tertiary outcome measure. The sample in each cross-section will include living patients only, so death will not be a problem as it would be in a longitudinal QOL study. We believe that this approach, along with our conservative assumptions regarding sessions needed as described previously, will largely prevent missing data for our primary outcome, as well as two secondary ones. Death will be tracked as an outcome, although the trial is not powered to assess this as a primary outcome. Data on subjects who leave the study site, will be used until their time of departure from the study. In other words, we will not track data for patients after they transfer to a non-study facility.

We will compare the characteristics of those with missing data to those without missing data, to test whether characteristics are similar between the groups. In addition to complete case analyses, we will use state-of-the-art statistical methods such as likelihood approaches and multiple imputation to deal with missing data.¹⁶⁰ These sensitivity analyses will assess the robustness of the results to missing data.

5.4.4 Handling of Withdrawals

If facilities do drop out during the intervention phase, they will be replaced and the intervention will take place at a new facility. A facility would need to be replaced if: 1) they request to leave the study; or 2) 75% of the staff do not complete at least 90 minutes of training within the first 14-16 weeks of the intervention period. Data will be retained for facilities that withdraw from the study, unless they explicitly request that the data not be used. It is important to note that patients who drop out of the patient activation intervention will not be dropped from the overall study unless requested, and collection of outcome measures will continue. Data will be retained for patients who opt out of the study after the initial opt out period up until the decision to opt

out, unless otherwise requested by the patient. Any attrition (lack of participation in the patient activation intervention) could contribute to a reduced estimate of treatment effect in analyses using the intent-to-treat principle; this reduction in estimated treatment effect would appropriately reflect the expected effect of this intervention in the general dialysis population.

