One wrinkle in the analysis of factorial designs is that interaction effects must be assumed to be null in order to test the main effects, but interaction effects are often of interest and are generally tested. Much has been written about this issue in the statistical literature; in practice, main effects are presented in the absence of a (statistically or clinically) significant interaction. When a statistically and clinically significant interaction is present, then the effect of each intervention is presented in the presence and absence of the other. Note that no other design can even test the presence of an interaction, so the simplicity gained by other analyses is at the cost of ignoring the possibility of interaction.

After the 12-week baseline period we plan to track outcomes for 36 weeks (24-week intervention period and 12-week post-intervention period). The parallel design with a 24-week intervention period, in assessing a post-intervention follow-up period, will generate valuable information related to the extent to which the intervention can sustain effects beyond an intensive implementation period. This meets the need for longer-term effectiveness studies of patient safety checklists.¹⁴⁷ This will also help clinics to understand an optimal schedule for intervention implementation.

III. Trial phase

The study is designed to be a cluster-randomized, pragmatic comparative effectiveness trial. As such, the trial will take place as part of routine HD care, with low-intensity patient follow-up and use of outcome data already gathered routinely by facilities.¹¹⁸ As such, this trial leverages unobtrusive existing electronic health record data to collect data regarding outcomes with the addition of two new data collection items to be collected through the electronic health record.¹⁴⁸

IV. Multi-center trial

The study will take place in 20 outpatient hemodialysis facilities operated by FMCNA. FMCNA has provided one site Principal Investigator for the complete study, since all sites are part of the same organization. All data from each of these facilities will be provided by FMCNA through its central corporate data warehouse, which aggregates data across FMCNA's digital documentation system. FMCNA will submit an IRB Authorization Agreement to cede IRB review and oversight to the University of Michigan.

V. Study Arms

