effect. (Further discussed in the heterogeneity of effects section). Although the study is not powered to detect even moderate interaction effects, it is possible that a strong interaction could be detected, and such an effect would be of interest.

The primary results will be based on the treatment effects tested in the initial models described for cluster-randomized trials with pre-planned covariates. Intent-to-treat analyses will be carried out, so that any deviations from the randomized interventions will not be taken into account in the primary test of treatment effects. Additionally, we will conduct as-treated analyses for the peer mentoring intervention whereby only patients who received peer mentoring are compared to patients in the other treatment arms, with adjustment for the same factors as in the intent-to-treat analyses. The small number of facilities (20) will preclude post-hoc adjustment for facility non-compliance with the interventions.

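### A withdrawing facility may ask that its data not be used; if invoked, this removes a randomised cluster after allocation and compromises the intent-to-treat analysis

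*Combined protocol and SAP*

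**What the plan says.** Section 5.4.4 keeps a withdrawn facility's data by default, with one exception: "Data will be retained for facilities that withdraw from the study, unless they explicitly request that the data not be used". The same section adds: "If facilities do drop out during the intervention phase, they will be replaced and the intervention will take place at a new facility". Sections 5.3, 5.4.3 and 11.4 also provide for replacement.

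Section 5.4.2 says: "Study participants and facilities will not be blinded to treatment status". Section 5.4.1 allocates 20 facilities, "assigning 5 facilities to each of the 4 combinations". On attrition, section 5.4.3 says: "we expect facility attrition to be very low". It gives no figure.

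The analysis principle is in section 11.4, under Aim 1: "Intent-to-treat analyses will be carried out, so that any deviations from the randomized interventions will not be taken into account in the primary test". The same statement is made again for Aims 1 and 2 together. Section 11.4 repeats the replacement rule but does not mention the data exception, and it does not say how a facility whose data are withheld, or its replacement, enters the analysis.

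Outcomes do not depend on the facility handing over records. Section 4.1 (IV) says: "All data from each of these facilities will be provided by FMCNA through its central corporate data warehouse". Under section 5.3, patients have their own opt-out.

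**The concern.** An intent-to-treat analysis of a cluster trial compares clusters as randomised. Here a facility that knows its arm, and can see how its own patients are doing, may leave and also take its data out of the comparison. That is an exclusion after randomisation, decided by the unit under evaluation. It covers about 60 patients who did not themselves opt out.

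The number of clusters is small, so each one counts. Lost precision is the lesser worry. The greater one is that, if the request is related to the facility's results, the remaining facilities are no longer the randomised ones and the estimate is biased.

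**Working it through.** **Do other provisions repair the loss?**

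- Replacement (sections 5.3, 5.4.3, 5.4.4, 11.4) adds a different facility. It does not return the excluded one.
- The imputation and likelihood methods (sections 5.4.3 and 11.4) follow a discussion of missing patient surveys. No sensitivity analysis for a removed facility is described.
- Section 11.4 says that 20 facilities are too few for post-hoc adjustment for facility non-compliance.

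**Inputs (section 11.2, Table 5).** 10 facilities per main-effect group, 60 patients each, intraclass correlation 0.10, SD 0.08 or 0.10, difference 0.034 to 0.043, significance level 0.05. Sidedness is not stated for the primary outcome; two-sided reproduces the table.

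**The plan's own power.** The design effect is 1 + 59 × 0.10 = 6.9, and SE = SD × √[(6.9/60) × (1/k₁ + 1/k₂)]. For SD 0.08 and 10 vs 10 facilities, SE = 0.08 × √(0.115 × 0.2) = 0.01213. Power = Φ(0.034/0.01213 − 1.96) = Φ(0.84) = 80%. All four entries reproduce:

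| Difference, SD | Table 5 | 10 vs 10 | 9 vs 10 | 9 vs 9 |
|---|---|---|---|---|
| 0.034, 0.08 | 80% | 80.0% | 77.9% | 75.8% |
| 0.034, 0.10 | 61% | 61.1% | 58.8% | 56.6% |
| 0.040, 0.08 | 91% | 90.9% | 89.4% | 87.9% |
| 0.043, 0.10 | 81% | 80.9% | 78.8% | 76.7% |

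One unreplaced facility costs 1.5 to 2.3 points. The table uses a normal approximation. A t test on facility means (18 df) gives 75.5% for the first row at 10 vs 10, and 72.9% at 9 vs 10 (17 df), so the loss is similar.

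**Spread of facility means.** SD × √(0.10 + 0.90/60) = SD × √0.115, which is 0.0271 (SD 0.08) or 0.0339 (SD 0.10): 2.7 to 3.4 percentage points.

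**Worst-case shift for one facility.** Assume no true effect, and that the facility removed is the one with the highest IDH rate on the intervention side of one margin. The expected maximum of 10 normal values is 1.54 SD.

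- No replacement: the mean of the other nine falls by 1.54/9 facility SDs, which is 0.46 to 0.58 points. Against targets of 3.4 and 4.3 points this is 0.46/3.4 and 0.58/4.3, about 14%.
- With a replacement drawn at random: 1.54/10 facility SDs, which is 0.42 to 0.52 points.

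**Error rate.** From 200,000 simulated null trials per setting, t test on facility means:

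| Removal | Two-sided error, SD 0.08 / 0.10 | In favour of intervention |
|---|---|---|
| Highest-IDH facility, no replacement | 7.36% / 7.47% | 6.1% |
| Highest-IDH facility, replaced | 7.11% / 7.25% | 5.8% |
| At random, no replacement | 4.94% / 4.98% | 2.5% |

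The signs follow from the assumption. By symmetry, removing the lowest-IDH intervention facility, or the highest-IDH facility on the comparison side, moves the estimate equally far the other way.

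**The case against.** Several points on the other side stand.

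- **The breach is conditional.** Retention is the default. A facility must both withdraw and explicitly ask, and attrition is expected to be very low. A reader might infer that section 5.4.4 contradicts the intent-to-treat statement outright. It does not: that statement speaks of deviations from the assigned intervention, and the conflict arises only if the exception is used. The text also says the data would not be used, not that they would be destroyed.
- **One facility is not 20% of what the powered tests compare.** A reader might take it that way from five facilities per combination. Table 5 powers 10 vs 10, so one facility is 10% of a margin. The 20% applies to cell comparisons, which Table 5 does not power, and section 11.4 says the study is not powered for even moderate interactions.
- **The direction of bias is not established.** A reader might infer that high-IDH or overburdened intervention facilities would leave, flattering the interventions. No text links IDH to withdrawal. The stated replacement triggers are a request to leave and insufficient staff training, and the Operations Committee feedback in section 10.1 concerns fidelity measures.
- **The exception may reflect an agreement.** Section 12 cites an attached data use agreement covering the parent organisation and the study facilities. It is not available here.
- **Patients have a similar option.** Section 5.4.4 also lets patients who opt out late ask for earlier data to be dropped. That is an individual's choice about one record, whereas the facility clause removes a randomised unit and patients who did not ask.

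These points limit likelihood and size. None tells the analyst what to do if a facility makes the request.

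**Conclusion.** The concern holds in conditional form. If a withdrawing facility invokes the exception, a randomised cluster is excluded after allocation by a party that knows its arm. The intent-to-treat analysis is then compromised, and neither replacement nor the missing-data plan repairs it.

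The expected power cost is small. Bias arises only if the request is related to outcome. The worst-case figures are an upper illustration for one facility, resting on the plan's SD and intraclass correlation, normally distributed facility means and no true effect; they are not a forecast. The clause should be corrected because the rule can be set now without knowledge of any facility's results, which will no longer be so once a request arrives.

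**What to change.** 1. In section 5.4.4, replace the exception with a statement that a facility may stop the intervention at any time, but data collected up to withdrawal stay in the primary intent-to-treat analysis under the original arm. Leave patient-level opt-out unchanged.
2. Put the same statement in the materials on which each facility's Governing Body approves participation.
3. In section 11.4, say how withdrawn and replacement facilities both enter the analysis. Include how the 60-session minimum applies: at three sessions a week it takes 20 weeks to reach, so if sessions are counted from the start of the intervention, a facility leaving earlier would contribute few or no patients to the primary model even with its data retained.
4. Where an existing data use agreement makes removal unavoidable, report the facility's arm and the timing of its withdrawal, and pre-specify a sensitivity analysis for its exclusion, for example placing the missing facility mean over a range around its arm's mean.

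The cost is a few sentences in the plan and the approval materials, plus a check of the data use agreement. The small downside is that a withdrawing facility loses the option to have its data not used.
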